3 INVESTIGATIONAL PLAN

This is a multi-center, uncontrolled observational study of patients who at the time of entry were prescribed with HUMIRA®(adalimumab) following normal clinical practice, with or without other anti-rheumatic treatments, prior to enrollment in this study.

Patients will be followed for 5 years within the post-marketing observational study.

Physicians will be provided with a study kit that includes a protocol, patient informed consent forms, adverse event report forms, and Data Report Forms (DRFs), for each patient to be enrolled. The participating physician will already have provided a prescription to the patient for HUMIRA®(adalimumab), along with instructions for appropriate use according to the European Union (EU) Summary of Product Characteristics (SPC).

Once the physician has determined that the patient meets the inclusion criteria, and the patient has agreed to be included in the observational study, the patient's baseline demographic data, and disease status will be reported in the Baseline DRF. The physician will then follow-up the patient via regular office visits at intervals as determined by routine clinical practice or as recommended by national guidelines.

Patient's safety and efficacy data if they are part of clinical routine will be recorded in the DRFs at Baseline, and regular visits which are closest to Month 3, Month 6, Month 9, Month 12, Month 18, Month 24, Month 30, Month 36, Month 42, Month 48, Month 54, and Month 60. While the physician will likely deem it appropriate and necessary to have the patient return for intermediate visits during the study period, data will be collected via DRFs only at the intervals which correspond closely to those described above. Physicians are encouraged to treat their patients as they would in their routine clinical practice. If treatment with HUMIRA®(adalimumab) is permanently discontinued for any reason, patients will be discontinued from the study and the reason should be recorded. Physicians will be asked to record adverse events up to 3 months after last administration of HUMIRA®(adalimumab) on the DRF of the next scheduled data collection time.

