3.1.1 Inclusion Criteria

- Patients with ongoing HUMIRA® (adalimumab) treatment who have been prescribed HUMIRA® (adalimumab) within local reimbursement guidelines.

- Patients must be willing to consent to data being collected and provided to Abbott Laboratories

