1. METHODOLOGY

The purpose of this statistical analysis plan is to provide detailed information on the statistical analysis of the data of the ProAct study. The plan is based on the quotation dated 18 October 2017 and the mail dated 4 April 2017.

1.1 *Study Objective*

To evaluate the effectiveness and safety of adalimumab for the treatment of rheumatoid arthritis (RA), psoriatic arthritis (PsA) and ankylosing spondylitis (AS) in real life clinical practice.

1.2 *Available data*

The questionnaires table, as received on 5 February 2018, contained 47378 records, of which 5947 baseline visits. This database has been adapted by hardcoding in the programmation in order to resolve inconsistencies, double patients, misclassification of visits, add additional visit CRF pages, add additional AE pages. A total of 5920 patients of which 2836 rheumatoid arthritis patients, 1127 psoriatic arthritis patients (of which 197 Oligoarticular PsA) and 1957 ankylosing spondylitis patients were included in the analysis.

The parameter DAS28 was entered in the database from the moment the new Belgium reimbursement criteria for Humira were in place (2010).

Visits were scheduled at baseline, months 3, 6, 9 and 12, then every 6 months till 5 years.

1.3 *Patient Population*

All patients are to be considered in the analysis.

1.4 *Data Handling*

All data handling rules used during the analysis will be described in the section Methodology of the Statistical Report.

‘LT’ visits are visits added in the database for patients who were lost to follow-up in order to close the patient in the database. These visits will not be taken into account for any analysis.

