1.5 Derived Data

- Study duration (year) = (visit date of last visit – visit date of baseline visit)/365.25

- Completed patients: patients with ≥ 1734 days study duration

- Treatment duration (year):

For completed patients:

(Date of last visit – Date of baseline visit)/365.25

For not completed patients:

Sum of number of weeks/52, months/12 and years patient has been on drug documented on the last visit

If missing: (Date of last visit – Date of baseline visit)/365.25

Note: Some patients stopped Humira temporally. The periods of not taken Humira are not taken into account for the analysis. These patients will be considered as having taken Humira during the complete study.

- Treatment duration category:

0 to 3 months

> 3 to 6 months

> 6 to 9 months

> 9 to 12 months

> 12 to 18 months

> 18 to 24 months

> 24 to 30 months

> 30 to 36 months

> 36 to 42 months

> 42 to 48 months

> 48 to 54 months

> 54 to 60 months

> 60 months

- For the purpose of the analysis of the evolution of parameters over time, follow-up visits will be classified into time windows, defined upon the number of days between Visit 1 and the date of each subsequent visit (PERIOD = Date of follow-up visit - Date of Visit 1)

- Period = Date of visit – Date of baseline visit

- Month 3 window: $1 \leq \text{period} \leq 137$ days

- Month 6 window: $138 \leq \text{period} \leq 228$ days

- Month 9 window: $229 \leq \text{period} \leq 319$ days

- Month 12 window: $320 \leq \text{period} \leq 456$ days

- Month 18 window: $457 \leq \text{period} \leq 639$ days

- Month 24 window: $640 \leq \text{period} \leq 821$ days

- Month 30 window: $822 \leq \text{period} \leq 1004$ days

- Month 36 window: 1005 <= period <= 1186 days
- Month 42 window: 1187 <= period <= 1368 days
- Month 48 window: 1369 <= period <= 1551 days
- Month 54 window: 1552 <= period <= 1733 days
- Month 60 window: 1734 <= period <= 1916 days

Each visit will be classified in a time window. If the date of the visit is completely missing, it will be assumed that the visit took place on the target day of the window as indicated on top of the follow-up page. If more than one follow-up visit is classified into the same time window, the visit closest to the target day is retained. If within a time window there are two visits at the same distance from the target day, the visit which comes first (e.g. before the target date) is retained. If there are two visits on the same date, the first record is retained.

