- BASDAI responder: a relative improvement in BASDAI of $\geq 50\%$
- DAS28 category: <2.6 , ≥ 2.6 and ≤ 3.2 , >3.2
- Serious adverse event = event where at least one criteria of seriousness is present
- An adverse event is considered to start in a certain year if the difference between start date and date of baseline (=AEPER) is in the following windows:
 - Year 1: $0 \leq \text{AEPER} < 365.25$
 - Year 2: $365.25 \leq \text{AEPER} < 730.5$
 - Year 3 $730.5 \leq \text{AEPER} < 1095.75$
 - Year 4: $1095.75 \leq \text{AEPER} < 1461$
 - Year 5: $1461 \leq \text{AEPER} < 1826.25$

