2 STATISTICAL ANALYSIS

The analysis of the baseline data and prior anti-TNF treatment will be performed broken down by indication (RA, PsA, AS). Within each indication, baseline data will also be presented broken down by completed/not completed patients. Statistical tests will be performed to compare baseline data for patients completed/not completed the study.

The analysis of treatment duration and the evolution of different parameters over time, will be performed broken down by indication (RA, PsA, AS).

The analysis of adverse events will be performed for all patients together and broken down by indication (RA, PsA, AS):

- Overall
- Per year (up to 5 years)
- By cumulative yearly period (till 5 years)
- Incidence
- Incidence divided by total exposure to treatment (till 5 years).
- Reason for seriousness
- Serious adverse events: number of patients and incidence by system organ class and preferred term
- Non-serious adverse events: number of patients by system organ class and preferred term

If an adverse event has no onset date, the observation date will be taken as onset date. Events that are coded with multiple MedDRA Terms will be counted as separate event.

The percentages in the adverse event table are calculated as follows:

Table	Nominator	Denominator
Number of patients with an adverse event per year.	Number of patients treated in that year with at least one adverse event in that year.	Number of patients treated in that year.
Number of patients with an adverse event per cumulative year	Number of patients with at least one adverse event in that year or before.	Number of patients.
Number of adverse events by total exposure to treatment	Number of adverse events in that year or before.	The sum of the patients' treatment exposure time in that year or before.

The following tables will be presented:

Rheumatoid Arthritis

- 1 Baseline Characteristics– All Patients and Broken Down by Early Termination**
 - 1.1 Age
 - 1.2 Gender
 - 1.3 Disease Duration Before Inclusion
 - 1.4 Anti-TNF use Before Inclusion
 - 1.4.1 Anti-TNF Naïve / Experienced
 - 1.4.2 Types of Anti-TNF use Before Inclusion
 - 1.5 Physician's Assessment of Disease Activity
 - 1.6 Clinical Examination
 - 1.6.1 Joint Assessment (tender joints count, swollen joints count)
 - 1.6.2 Inflammatory Parameters (CRP, ESR)
 - 1.6.3 Physical Function (HAQ %)
 - 1.7 Concomitant Medication
 - 1.7.1 Concomitant Steroids
 - 1.7.2 Concomitant NSAIDs
 - 1.7.3 Concomitant Immunomodulators

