 - 1.7.4 Number of DMARDs Used
 - 1.7.5 Frequency of Use of Each Type of DMARD
 - 1.7.6 Combination of Types of DMARD Used
 - 1.8 Study Duration
 - 1.9 Results of the Tests

- 2 Follow-up Data**
 - 2.1 Treatment Duration
 - 2.1.1 Treatment Duration
 - 2.1.2 Treatment Duration Category
 - 2.1.3 Treatment Duration Broken Down by Year of Start Treatment
 - 2.1.4 Treatment Duration Broken Down by DAS28 Category at Window 2 (Month 6)
 - 2.2 Physician's Assessment of Disease Activity
 - 2.2.1 Physician's Assessment of Disease Activity in Each Window
 - 2.2.2 Physician's Assessment of Disease Activity - Difference from Baseline
 - 2.3 Clinical Examination
 - 2.3.1 Joint Assessment (tender joints count, swollen joints count) in Each Window
 - 2.3.2 Joint Assessment (tender joints count, swollen joints count) – Difference from Baseline
 - 2.3.3 Inflammatory Parameters (CRP, ESR) in Each Window
 - 2.3.4 Inflammatory Parameters (CRP, ESR) – Difference from Baseline
 - 2.3.5 Physical Function (HAQ %) in Each Window
 - 2.3.6 Physical Function (HAQ %) – Difference from Baseline
 - 2.3.7 Physical Function (HAQ %) - Number of Patients with >7.33% Reduction from Baseline
 - 2.3.8 DAS28 in Each Window
 - 2.3.9 DAS28 – Difference From Baseline
 - 2.3.10 DAS28 Category in Each Window

3 Adverse Events

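### Adverse event years run from the enrolment visit in patients already on adalimumab, so tables 3.2, 3.3 and 3.5 may misstate risk by year of treatment

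*SAP*

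**What the plan says.** **Time origin.** SAP 1.5 (Derived Data): "An adverse event is considered to start in a certain year if the difference between start date and date of baseline (=AEPER") lies in the stated window. Year 1 starts at day 0 and Year 5 ends before day 1826.25, all counted from the baseline visit.

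**Who is enrolled.** Protocol 3.1.1: "Patients with ongoing HUMIRA® (adalimumab) treatment who have been prescribed HUMIRA® (adalimumab) within local reimbursement guidelines". Protocol 3 adds that patients had their prescription, "with or without other anti-rheumatic treatments, prior to enrollment in this study". Neither section sets a minimum or maximum time already on drug, and the exclusions in Protocol 3.1.2 do not either.

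**Who is analysed.** SAP 1.3: "All patients are to be considered in the analysis".

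**How the tables are built.** In SAP 2 the per-year numerator is "Number of patients treated in that year with at least one adverse event in that year", over the patients treated in that year. The table list splits adverse events by indication, year, cumulative year and exposure, but never by time since first injection. Anti-TNF use before inclusion appears only among the baseline tables. The start of treatment appears only in table 2.1.3, "Treatment Duration Broken Down by Year of Start Treatment".

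**Treatment duration.** SAP 1.5 uses "Date of last visit – Date of baseline visit)/365.25" for completed patients. For the others it uses "Sum of number of weeks/52, months/12 and years patient has been on drug documented on the last visit", and falls back on the visit dates if that is missing.

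**The concern.** A table of adverse events by year, in a long-term safety study of one drug, invites reading as risk by year of treatment. Here the clock starts at enrolment. A patient enrolled in the third year on drug puts third-year events into Year 1. A patient who stopped for an adverse event before enrolment cannot meet the ongoing-treatment criterion and is never seen, so any established user enters already selected for tolerating the drug.

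At stake is the shape of the safety profile over time, which matters for a study whose objective is long-term use and safety. Table 2.1.3 raises a related question. If start year means year of first injection, patients who started well before enrolling had to remain on drug until they enrolled, and start-year groups could differ in duration for that reason alone.

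**Working it through.** **1. The plan's own figures.** The year limits are k × 365.25 for k = 1 to 5: 365.25, 730.5, 1095.75, 1461 and 1826.25. They match SAP 1.5. The patient total in SAP 1.2 also reproduces: 2836 + 1127 + 1957 = 5920. The rule is arithmetically sound; only its origin is in question.

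**2. Inputs for the size.** Two quantities are needed and neither document gives them, so both are assumptions:
- f, the share of patients already on drug at baseline, here taken to have at least 12 months of prior use;
- r, the event rate in the first year on drug divided by the later rate.

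Let a be the first-year rate and b = a/r the later rate. The observed Year 1 rate is (1 − f)a + fb. Divided by a, this is

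ratio = (1 − f) + f/r.

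| r | f = 25% | f = 50% | f = 75% |
|---|---|---|---|
| 0.5 | 1.25 | 1.50 | 1.75 |
| 1 | 1.00 | 1.00 | 1.00 |
| 1.5 | 0.917 | 0.833 | 0.75 |
| 2 | 0.875 | 0.75 | 0.625 |
| 3 | 0.833 | 0.667 | 0.50 |

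For r = 2 the shortfalls are 1 − 0.875 = 12.5%, 25% and 37.5%. Over r = 1.5 to 3 they run from about 8% to 50%. At r = 1 there is no error, and at r = 0.5 Year 1 is too high by 25% to 75%. At f = 0 the ratio is 1 for every r.

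**3. Shorter prior use.** A patient enrolled m months after first injection (m up to 12) spends w = (12 − m)/12 of study Year 1 in the first treatment year. For that patient the ratio is w + (1 − w)/r. With r = 2:
- m = 1: 0.917 + 0.083/2 = 0.958, or 4% low;
- m = 3: 0.75 + 0.25/2 = 0.875, or 12.5% low;
- m = 4: 0.667 + 0.333/2 = 0.833, or about 17% low;
- m = 6: 0.5 + 0.5/2 = 0.75, or 25% low;
- m = 12: 0 + 1/2 = 0.5, or 50% low.

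If half the cohort entered at month 4 and the rest at first injection, the cohort ratio is 0.5 + 0.5 × 0.833 = 0.917, about 8% low. The 12-month case in step 2 gives 25% at the same share.

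**4. The exposure denominator.** The duration rule for non-completers does not say that documented time on drug is limited to time after baseline. If it includes p years before enrolment and t years after, table 3.5 could carry p + t years in the denominator, while events before baseline have negative AEPER and fall in no year. The patient's rate is then multiplied by t/(t + p). With p = 1 and t = 2 (assumed), this is 2/3 = 0.67.

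**5. Table 2.1.3.** SAP 1.5 does not define start year. It could be the first-injection year or the enrolment year. The duration being tabulated runs from baseline for completers and possibly from first injection for non-completers.

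**The case against.** The strongest reply is that the SAP treats baseline as the start of treatment, or close to it. Completers' treatment time runs from baseline. Patients are classed as anti-TNF naïve or experienced at inclusion. BASDAI response and HAQ reduction from baseline, and visits at months 3, 6, 9 and 12, all suit new starters. A prescription before enrolment may precede it by days. The SAP also defines its years openly from baseline, nowhere calls them treatment years, and belongs to a descriptive study; rates by year since enrolment validly describe the enrolled cohort.

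Much of this stands. It rules out any claim about how many prior users there are, and the tables are not wrong as descriptions of follow-up. It does not close the gap. No criterion limits prior use, the wording on ongoing treatment admits it, and no planned output would show a reader how much there was.

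Two stronger readings are tempting, and the documents support neither:
- **That Year 1 understates early risk.** This needs both material prior use and a rate that is higher early on drug. Neither is reported, and the error reverses if the rate rises with time on drug. The large user numbers in the protocol's introduction come from other programmes and say nothing about who enrolled here.
- **That table 2.1.3 will show a spurious difference by start year.** With assumed stopping hazards of 0.25 in the first year and 0.10 per year afterwards, mean five-year duration from enrolment is 0.885 + 0.779 × 3.297 = 3.45 years for new users and 3.93 for those at least a year on drug. That assumes duration from enrolment for everyone, which is not the SAP's main rule for non-completers, and that start year is not simply the enrolment year.

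Feasibility is also a fair challenge. The baseline items in Protocol 3.3.3, 3.3.4 and 3.3.7 name no first-injection date, and a calendar year alone cannot support a cut in months.

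**Conclusion.** The concern holds as a mismatch between the time axis and its likely reading. Adverse event years are years since enrolment, in a cohort that may mix new starters with established users selected for tolerance, and no table separates them. The tables may therefore misstate risk by year of treatment, in a direction that depends on the event type.

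The size cannot be fixed from the documents. The 12.5%, 25% and 37.5% shortfalls are illustrations. They rest on an assumed twofold rate ratio, assumed shares of 25%, 50% and 75%, and at least 12 months of prior use in every prior user. Shorter prior use shrinks them. The missing time origin in table 2.1.3 and the two duration rules are points to clarify, not demonstrated biases.

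**What to change.** 1. Label the columns of tables 3.2, 3.3 and 3.5 as year since enrolment. This needs no data.
2. Report the distribution of time from first injection to baseline by indication, using the start information that table 2.1.3 already needs.
3. Present tables 3.2, 3.3 and 3.5 separately for recent starters, later enrolees and patients with unknown start. If start dates are recorded, cut at 3 months from first injection to enrolment. If only the year is recorded, compare start year with enrolment year.
4. State whether start year in table 2.1.3 is the first-injection year or the enrolment year. If the former, restrict the table to recent starters or show the two groups separately.
5. Use one time origin for treatment duration in completers and non-completers, so that the table 3.5 denominator covers the same period as its events.
6. State as a limitation that patients who stopped before enrolment are not observed. No split can recover them.

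The cost is SAP wording, one derived variable and one extra split. The downside is smaller groups, most felt in psoriatic arthritis (1127 patients), and an unknown category that could be large if start information is sparse.

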2 STATISTICAL ANALYSIS

The analysis of the baseline data and prior anti-TNF treatment will be performed broken down by indication (RA, PsA, AS). Within each indication, baseline data will also be presented broken down by completed/not completed patients. Statistical tests will be performed to compare baseline data for patients completed/not completed the study.

The analysis of treatment duration and the evolution of different parameters over time, will be performed broken down by indication (RA, PsA, AS).

The analysis of adverse events will be performed for all patients together and broken down by indication (RA, PsA, AS):

- Overall
- Per year (up to 5 years)
- By cumulative yearly period (till 5 years)
- Incidence
- Incidence divided by total exposure to treatment (till 5 years).
- Reason for seriousness
- Serious adverse events: number of patients and incidence by system organ class and preferred term
- Non-serious adverse events: number of patients by system organ class and preferred term

If an adverse event has no onset date, the observation date will be taken as onset date. Events that are coded with multiple MedDRA Terms will be counted as separate event.

The percentages in the adverse event table are calculated as follows:

Table	Nominator	Denominator
Number of patients with an adverse event per year.	Number of patients treated in that year with at least one adverse event in that year.	Number of patients treated in that year.
Number of patients with an adverse event per cumulative year	Number of patients with at least one adverse event in that year or before.	Number of patients.
Number of adverse events by total exposure to treatment	Number of adverse events in that year or before.	The sum of the patients' treatment exposure time in that year or before.

The following tables will be presented:

Rheumatoid Arthritis

- 1 Baseline Characteristics– All Patients and Broken Down by Early Termination**
 - 1.1 Age
 - 1.2 Gender
 - 1.3 Disease Duration Before Inclusion
 - 1.4 Anti-TNF use Before Inclusion
 - 1.4.1 Anti-TNF Naïve / Experienced
 - 1.4.2 Types of Anti-TNF use Before Inclusion
 - 1.5 Physician's Assessment of Disease Activity
 - 1.6 Clinical Examination
 - 1.6.1 Joint Assessment (tender joints count, swollen joints count)
 - 1.6.2 Inflammatory Parameters (CRP, ESR)
 - 1.6.3 Physical Function (HAQ %)
 - 1.7 Concomitant Medication
 - 1.7.1 Concomitant Steroids
 - 1.7.2 Concomitant NSAIDs
 - 1.7.3 Concomitant Immunomodulators
 - 1.7.4 Number of DMARDs Used
 - 1.7.5 Frequency of Use of Each Type of DMARD
 - 1.7.6 Combination of Types of DMARD Used
 - 1.8 Study Duration
 - 1.9 Results of the Tests

- 2 Follow-up Data**
 - 2.1 Treatment Duration
 - 2.1.1 Treatment Duration
 - 2.1.2 Treatment Duration Category
 - 2.1.3 Treatment Duration Broken Down by Year of Start Treatment
 - 2.1.4 Treatment Duration Broken Down by DAS28 Category at Window 2 (Month 6)
 - 2.2 Physician's Assessment of Disease Activity
 - 2.2.1 Physician's Assessment of Disease Activity in Each Window
 - 2.2.2 Physician's Assessment of Disease Activity - Difference from Baseline
 - 2.3 Clinical Examination
 - 2.3.1 Joint Assessment (tender joints count, swollen joints count) in Each Window
 - 2.3.2 Joint Assessment (tender joints count, swollen joints count) – Difference from Baseline
 - 2.3.3 Inflammatory Parameters (CRP, ESR) in Each Window
 - 2.3.4 Inflammatory Parameters (CRP, ESR) – Difference from Baseline
 - 2.3.5 Physical Function (HAQ %) in Each Window
 - 2.3.6 Physical Function (HAQ %) – Difference from Baseline
 - 2.3.7 Physical Function (HAQ %) - Number of Patients with >7.33% Reduction from Baseline
 - 2.3.8 DAS28 in Each Window
 - 2.3.9 DAS28 – Difference From Baseline
 - 2.3.10 DAS28 Category in Each Window

3 Adverse Events

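### The cumulative AE percentage counts patients lost to follow-up as AE-free to year 5, and exposure for non-completers has no start point that lets it be split by the baseline-anchored AE years

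*SAP*

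**What the plan says.** The SAP, section 2, sets out numerators and denominators for three AE tables.

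- **Per year:** "Number of patients treated in that year with at least one adverse event in that year", over the patients treated in that year.
- **Cumulative:** "Number of patients with at least one adverse event in that year or before", over the number of patients, with no restriction to those still observed.
- **By exposure:** events to date over "The sum of the patients' treatment exposure time in that year or before".

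SAP 1.5 anchors the AE years at baseline: "An adverse event is considered to start in a certain year if the difference between start date and date of baseline" falls in the stated limits, with year 5 ending at day 1826.25. It defines one exposure-type variable, treatment duration:

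- For completers (at least "1734 days study duration") it is baseline visit to last visit.
- For non-completers it is "Sum of number of weeks/52, months/12 and years patient has been on drug documented on the last visit".
- Only if that record is missing does a non-completer get baseline to last visit.

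SAP 1.4 describes LT visits, entered to close patients who were lost to follow-up, and excludes them from all analyses. Protocol 3.1.1 enrols patients already on treatment. Protocol 3 ends participation at permanent discontinuation and collects AEs for up to 3 months after the last administration.

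**The concern.** Long-term safety is a stated objective of the protocol, and these tables are how it is reported.

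The per-year row adjusts its denominator for attrition and the cumulative row does not. A patient lost early without an AE stays in the cumulative denominator as if observed to year 5. Nothing labels the result a crude proportion, so a reader may take it as a 5-year risk.

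The exposure row is the natural remedy for attrition, but its denominator is not fully specified. The clock depends on whether the patient completed and on whether the recorded time is missing. For non-completers the total has no start point, so it cannot be placed in years 1 to 5 without a rule that the SAP does not give. Deciding who was treated in a given year needs the same placement. AEs in the 3 months after the last dose can enter the numerator with no statement on whether that time counts below.

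**Working it through.** **The plan's own figure.** The fixed denominator reproduces: 2836 + 1127 + 1957 = 5920. The documents give no AE rate, exit rate, loss count or person-years, so everything below is illustrative.

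**1. Cumulative table**

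*Exit hazard.* SAP 1.2 gives 47,378 records, of which 5,947 are baseline visits, before correction of the database. Follow-up records per patient are (47,378 − 5,947)/5,947 = 6.97, against 12 planned. The shortfall mixes exits with skipped visits, because data come only from routine visits. For an assumed skipped share s, the constant exit hazard L solves (1 − s) × Σ exp(−L·t) = 6.967 over t = 3, 6, 9, 12, 18, …, 60 months. L reaches 0 at s = 1 − 6.967/12 = 0.419.

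*Crude 5-year proportion.* With first-AE hazard h, this is h/(h+L) × [1 − exp(−5(h+L))].

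*Aalen-Johansen value.* Replace L by L × (1 − share of exits that are losses). Losses are censored and other exits compete. This assumes that loss is unrelated to AE risk.

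With h = 0.10 per year (assumed):

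| Skipped visits | L per year | Crude | Aalen-Johansen, 1/3 lost | Gap, 1/3 lost | Gap, 2/3 lost |
|---|---|---|---|---|---|
| 0% | 0.263 | 23.1% | 27.2% | 4.1 points | 9.4 |
| 20% | 0.146 | 28.8% | 31.8% | 3.0 | 6.5 |
| 30% | 0.082 | 32.8% | 34.8% | 2.0 | 4.2 |
| 40% | 0.014 | 38.1% | 38.5% | 0.4 | 0.8 |

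If no exits are losses, the gap is 0 in every row. At h = 0.03 and one third lost it is 1.5, 1.1, 0.7 and 0.2 points.

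**2. Exposure clock**

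| Patient | Start of clock | End of clock |
|---|---|---|
| Completer | Baseline | Last visit |
| Non-completer, time recorded | Not stated | Not stated |
| Non-completer, time missing | Baseline | Last visit |
| AE years | Baseline | Day 1826.25 |

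Only the second row cannot be laid over the AE years. Completers can also run past the last AE year: the month 60 window extends to day 1916.

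**3. Direction of any bias in the rate**

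Pre-baseline time would inflate the denominator. Post-dose events without matching time would inflate the numerator. To see whether one dominates, take:

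- mean exposure m = (1 − exp(−5L))/L;
- non-completers q = 1 − exp(−L × 1734/365.25);
- assumed, 10% to 30% of non-completers carrying 1 to 2 pre-baseline years;
- assumed, two thirds to all of non-completers having a 3-month AE tail at an unchanged AE hazard.

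At L = 0.263, m = 2.78 and q = 0.713. The pre-baseline share runs from 0.1 × 1 × 0.713/2.78 = 2.6% to 0.3 × 2 × 0.713/2.78 = 15.4%. The tail share runs from 0.25 × (2/3) × 0.713/2.78 = 4.3% to 0.25 × 0.713/2.78 = 6.4%. The rate is then 1.043/1.154 = 0.90 to 1.064/1.026 = 1.04 times the matched rate. At L = 0.082 the range is 0.97 to 1.01. Both ranges span 1.

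**The case against.** The cumulative numerator and denominator are printed in full, and protocol 5.1.2 promises frequencies and percentages, so nothing is hidden or miscalculated. Because permanent discontinuation ends participation, the fixed denominator gives a valid on-study cumulative incidence except where patients are lost. The per-year table also responds to attrition. All of this stands, and it is why the crude table can stay.

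Three stronger readings are tempting, and the documents support none of them.

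- *The table misses the full 5-year risk.* Censoring every exit gives much larger gaps: at an assumed hazard of 0.05 per year and 50% exit, 16.2% crude against 22.1%. That treats discontinuation as if treatment had continued, which is a different question from on-study incidence.
- *Non-completers' exposure includes time before baseline, so the rate is too low.* Entry on ongoing treatment makes this possible, but no passage shows it. The baseline-anchored fallback and the 5-year limit on the exposure analysis suggest that on-study time is meant. Nor does the SAP say outright that treatment exposure time is the treatment duration of section 1.5; it is only the one candidate defined. Recorded time may even be the better measure for a patient who stopped drug before the last visit.
- *The record counts reveal the exit rate.* They precede correction, and their make-up is uncertain. If they include one termination record per patient, the exit hazard at 40% skipped visits becomes 0.083 instead of 0.014, and the gap 2.0 points instead of 0.4.

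SAP 1.4 leaves data handling rules to the Statistical Report, so a splitting rule may appear there. A safety denominator should be fixed in the SAP, not described afterwards.

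**Conclusion.** The point holds and should be fixed, with medium confidence.

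The cumulative percentage understates on-study cumulative incidence to the extent that exits are losses. At an assumed AE hazard of 0.10 per year with one third of exits lost, that is about 0.4 to 4 points at year 5. The gap is larger if more exits are losses, smaller for rarer events, and zero if there are none. The documents establish that losses occurred but not how many.

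The exposure denominator cannot be split by year as written, because the clock for non-completers has no start point and differs by completion status and missingness. Post-dose events have no matching exposure rule. These are gaps in specification. Whether they bias the rate, and in which direction, is unknown.

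**What to change.** **(a) Cumulative table.** Keep it and label it a crude proportion of all patients. Add a descriptive Aalen-Johansen cumulative incidence at years 1 to 5 for any, serious, fatal and discontinuation-causing AEs, without tests, in line with protocol 5. Censor lost patients at the last non-LT visit. Treat permanent discontinuation and death as competing events where they are not the event itself.

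**(b) Exposure rate.** Keep it as a rate per treatment exposure. Count exposure from the baseline visit for every patient, cap it at the time from baseline to the last non-LT visit and at day 1826.25, and split it at the AE year limits of SAP 1.5. Use the same placement to decide who was treated in each year. Either count only AEs inside the exposure window, or show the rate with and without the 3-month post-dose events and time, labelled as such.

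**(c) Check only.** For non-completers, tabulate recorded time on drug against baseline-to-last-visit time. Recorded time is pre-baseline time plus treated time on study, and the latter cannot exceed baseline to last visit. An excess beyond rounding would therefore indicate pre-baseline time. No excess would not rule it out, since a patient who stopped before the last visit can carry earlier time unseen. The table "Treatment Duration Broken Down by Year of Start Treatment" may help, but the SAP does not define that start year and it could be the baseline year.

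**Cost.** SAP wording and some reprogramming. The protocol asks for the administration schedule and the reason for withdrawal but does not promise a last-administration date, so stop dates will be approximate for some patients; report how many. Some figures may be slightly less favourable.
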